##### 9.4.1.2 Analysis methods

The descriptive statistics of CDE at Visit 00 (surgery day) will be calculated for each of the surgical techniques (arithmetic mean, standard deviation, N, median, minimum and maximum) and the means will be estimated using 95% confidence intervals based on the MMRM (mixed model for repeated measures). The superiority of LenSx to Conventional will be tested if there is a significant difference in mean between the surgical techniques (MMRM-based t-test, significance level: one-sided 2.5%).

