### 4.3 Statistical Methods for Efficacy Analyses

The superiority of LenSx to Conventional surgery will be tested if there is a significant difference in mean between the surgical techniques (MMRM-based t-test, significance level: one-sided 2.5%). The descriptive statistics of CDE at Visit 00 (surgery day) will be calculated by each surgical techniques (arithmetic mean, standard deviation, N, median, minimum and maximum) and the means will be estimated using 95% confidence intervals based on the MMRM (mixed model for repeated measures).

The hypothesis on percent ECD change from preoperative visit to Visit 5 (150-210 days after surgery) will be tested only if the superiority is demonstrated in the primary analysis. The

hypothesis on average torsional amplitude at Visit 00 (surgery day) will be tested only if there is a significant difference in percent ECD change (both MMRM-based t-test, significance level: one-sided 2.5%). The descriptive statistics of ECD, absolute and percent ECD change and average torsional amplitude will be calculated for each of the surgical techniques (arithmetic mean, standard deviation, N, median, minimum and maximum) and the means will be estimated using 95% confidence intervals based on the MMRM (mixed model for repeated measures). The following is the SAS psuedo code for the primary and secondary analyses.

```
PROC MIXED ;
  CLASS surgery subjid ;
  MODEL y = surgery / DDFM=KR ;
  RANDOM subjid ;
  LSMEANS surgery / CL DIFFS ;
RUN ;
```

[figure not shown]

Table. 4–1 summarizes the key efficacy analyses.

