#### 4.4 Multiplicity Strategy

In the primary analysis, multiplicity will not be an issue since there is only one primary endpoint. For the 2 secondary endpoints, the hypotheses will be tested in the pre-specified order only if the superiority is demonstrated in the primary analysis. Therefore, the type I family-wise error (FWE) for the total of 3 hypothesis tests (primary analysis (once) and secondary analysis (twice)) is controlled (one-sided 2.5%). No hypothesis test is planned for any of the other exploratory endpoints.

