## **7 Sample Size and Power Calculations**

The 50 evaluable subjects will be enrolled for this study. For CDE, treatment difference was assumed 1.9% with common standard deviation of 1.2%. The sample size was simulated in Table. 7-1 varying correlation coefficient between both eyes because intra-subject positive correlation between both eyes is assumed for endpoints in this study.

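### The SAP's random-intercept code forces equal variances in the two arms: the arm-mean confidence intervals are mis-sized if the arm SDs differ, and the test level is slightly exceeded if fellow-eye correlation is near zero

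*SAP*

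**What the plan says.** SAP 4.3 gives one block of SAS pseudo code for CDE, percent ECD change and average torsional amplitude. The mean model is "MODEL y = surgery / DDFM=KR" and the only covariance statement is "RANDOM subjid". There is no REPEATED statement, no arm-specific variance and no option allowing a negative covariance. SAP Table 4-1 says only MMRM. The sensitivity analyses change the analysis set, not the model.

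Two outputs come from this model:
- the test of the difference ("MMRM-based t-test, significance level: one-sided 2.5" per cent);
- an interval for each arm: "the means will be estimated using 95% confidence intervals based on the MMRM (mixed model for repeated measures"). Protocol 9.4.1.2 asks for the same: "the means will be estimated using 95% confidence intervals based on the MMRM".

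SAP 4.4 states that family-wise error over the three tests is held at one-sided 2.5%. For planning, SAP 7 says: "The 50 evaluable subjects will be enrolled for this study" and "For CDE, treatment difference was assumed 1.9% with common standard deviation of 1.2" per cent. It assumes a common SD of 11% for ECD and a positive correlation between eyes, and tabulates power for correlations from 0 to 0.99.

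**The concern.** A random intercept with one residual variance is compound symmetry: both arms share a variance, and the fellow-eye covariance is the intercept variance. PROC MIXED by default holds that variance at zero or above. This is software behaviour inferred from the absence of an override, not SAP text.

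Three consequences follow.
- Each arm's interval uses a pooled SD, so if the arms differ one interval is too narrow and the other too wide.
- When the sample covariance is negative, the fit falls back to an unpaired test with a smaller standard error than the paired test, which raises the level.
- The FAS is defined by eye (SAP 2.1), so single eyes may enter. The equal-variance assumption then also reaches the treatment difference.

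At stake are the reported error bars and, at low correlation, the exactness of the alpha claim.

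**Working it through.** **Inputs.** 50 pairs, CDE difference 1.9 with SD 1.2, ECD difference 5.5 with SD 11, correlations 0 to 0.99 (SAP 7); one-sided 2.5% (SAP 4.3). The only arm-specific CDE SDs in the documents are in the package insert (Protocol Appendix B), laser vs manual: 2.757 vs 2.159 (moderate) and 5.119 vs 4.487 (hard).

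**1. Stated power.** Paired t-test, SE = SD·√(2(1−ρ)/50), 49 df, noncentral t. For ECD at ρ = 0, SE = 11·√(2/50) = 2.2 and the noncentrality is 5.5/2.2 = 2.5. Power at the five tabulated correlations is 0.688, 0.808, 0.934, 0.998 and >0.999, as in SAP Table 7-2. CDE power is >0.999 throughout. The tables therefore describe a paired t-test.

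**2. What the code does with complete pairs.** Let s₁², s₂² and c be the sample variances and covariance.
- If c > 0: SE² of the difference = (s₁² + s₂² − 2c)/50 with 49 df, which is the paired t-test.
- If c ≤ 0: SE² = (s₁² + s₂²)/50, taken with 98 df. This is smaller than the paired value when c < 0.
- In both cases SE² of each arm mean = (s₁² + s₂²)/(2·50).

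**3. Arm-mean intervals.** Large-sample coverage is 2Φ(1.96·pooled SD/arm SD) − 1.

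| SDs (LenSx, Conventional) | Pooled SD | Ratios pooled/arm | Simulated coverage |
|---|---|---|---|
| equal | – | 1, 1 | 95.0%, 95.0% |
| 2.757, 2.159 | √((7.601+4.661)/2) = 2.476 | 0.898, 1.147 | 92.2%, 97.5% |
| 5.119, 4.487 | √((26.204+20.133)/2) = 4.813 | 0.940, 1.073 | 93.5%, 96.4% |

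Correlation makes no material difference to these figures.

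The SAP model pools grades. The insert gives no numbers per grade, so a mix must be assumed. With equal shares, the LenSx variance is 0.5·7.601 + 0.5·26.204 + 0.25·(8.666−6.170)² = 18.46 (SD 4.30). The Conventional variance is 0.5·4.661 + 0.5·20.133 + 0.25·(10.749−7.242)² = 15.47 (SD 3.93). The SD ratio is 1.09. For splits of 65 pairs from 10/55 to 55/10 it is 1.09 to 1.14, and coverage is about 93.5 to 94% and 96 to 96.5%.

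**4. Level of the difference test.** Simulation of 50 complete pairs with equal SDs, at least one million trials per setting, applying step 2:

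| ρ | One-sided level of coded model |
|---|---|
| −0.10 | 3.2% |
| 0 | 2.8% |
| 0.05 | 2.7% |
| 0.10 | 2.6% |
| 0.20 and above | 2.5% |

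At ρ = 0 the zero bound is reached in 50% of trials. With 49 df at the bound the level there is 2.75%. The paired t-test stays at 2.5% throughout. Unequal SDs add no error to this test when pairs are complete.

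**5. Single eyes.** Take 5 LenSx eyes missing, moderate-grade SDs and ρ = 0.
- True SE = √(7.601/45 + 4.661/50) = 0.5120.
- Model SE = √[((45·7.601 + 50·4.661)/95)·(1/45 + 1/50)] = 0.5056.
- Level = Φ(−1.96·0.5056/0.5120) = 2.65%.

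The result is the same at ρ = 0.25 and 0.5. With 10 LenSx eyes missing it is about 2.8%. If 5 Conventional eyes are missing instead, it is 2.36%, so the direction depends on which arm loses eyes.

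**6. Decisions.** At the planned effects and ρ = 0 the expected t is 1.9/(1.2·√(2/50)) = 7.9 for CDE and 2.5 for ECD. ECD power at ρ = 0 is about 0.71 under the code against the stated 0.688.

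**The case against.** The plan assumes a common SD, and on that assumption the arm intervals cover correctly at every correlation tried. The SD evidence is thin. These are sample SDs within single grades, from chop and cylinder patterns, whereas Protocol 6.4 sets a 200 µm fragmentation grid. The insert reports no test of the CDE SDs.

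Near-zero correlation is also not what the plan expects. SAP 7 assumes positive correlation, Protocol 4.3 excludes patients whose eyes differ in grade, and Appendix C has one surgeon do all the phacoemulsification. The insert's paired p-values (0.0378 and 0.0194) allow a rough check: SD of the difference = mean difference·√n/t, and r = (s₁² + s₂² − SD²)/(2s₁s₂) within each grade. With both grades combined, over the assumed splits above, CDE correlation comes out at about 0.19 to 0.57.

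Success rests on the difference, not on the arm intervals, and arm-specific means, SDs and Ns are reported anyway. The code is labelled as pseudo code.

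Most of this stands and sets the severity. It does not remove the point. The pseudo code is the only covariance specification in the plan, the arm intervals are stated outputs, and positive correlation does not correct them if the SDs differ. The documents give no fellow-eye correlation estimate for ECD change.

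**Conclusion.** The point holds conditionally and is of low severity. The arm-mean intervals are mis-sized only if the arm SDs differ. Under the insert's CDE SDs the loss for LenSx is about 1.5 to 3 percentage points of coverage, and probably less with grades pooled. The level is slightly exceeded only if correlation is near zero or negative, or possibly if single eyes enter and the SDs differ. The level figures assume the default zero bound and, at that bound, 98 df.

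A reader might infer that the intervals for all three endpoints will fail to cover at 95%. The documents do not support that: the planning assumption is a common SD, and no arm-specific SDs are given for ECD or torsional amplitude. Nor does low correlation or the zero bound mis-size the arm intervals.

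A reader might also infer that the primary conclusion or alpha control is seriously compromised. It is not: the excess is at most about 0.3 percentage points at ρ = 0 with complete pairs, and an expected t of 7.9 leaves the CDE decision unaffected. A borderline ECD result, which also gates torsional amplitude, is the one place where a decision could change.

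Single eyes may enter rather than will, because Protocol 4.3 words the intraoperative exclusion by patient.

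**What to change.** In SAP 4.3 replace the statement "RANDOM subjid" with `REPEATED surgery / SUBJECT=subjid TYPE=UN ;` and keep the Kenward-Roger and LSMEANS parts. State there how incomplete pairs are handled. For complete pairs this is the paired t-test: one-sided level 2.5% at every correlation tried and 95.0% coverage in each arm whatever the SD ratio. Single eyes still contribute.

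The cost is one line of SAP code and no new data. The one downside is that ECD power at ρ = 0 becomes the stated 0.688 rather than about 0.71, and part of that gap came from the inflated level. At ρ = 0.5 and above the coded model and the replacement have the same power.

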**Table. 4–1 Summary of Analysis Strategy for Key Efficacy Endpoints**

Endpoint	Main vs. Sensitivity Approach a	Statistical Method b	Analysis Set	Missing Data Approach
Primary				
CDE at Visit 00	M	MMRM c	FAS	Observed data only
CDE at Visit 00	S	MMRM c	MFAS	Observed data only
CDE at Visit 00	S	MMRM c	PPS	Observed data only
Secondary				
Percent ECD change at Visit 5	M	MMRM c	FAS	Observed data only
Percent ECD change at Visit 5	S	MMRM c	MFAS	Observed data only
Percent ECD change at Visit 5	S	MMRM c	PPS	Observed data only

Average Torsional Amplitude at Visit 00	M	MMRM c	FAS	Observed data only
Average Torsional Amplitude at Visit 00	S	MMRM c	MFAS	Observed data only
Average Torsional Amplitude at Visit 00	S	MMRM c	PPS	Observed data only

██████████
 
aM=Main analysis approach; S=Sensitivity analysis approach  bFurther details on statistical models are:  c Mixed model for repeated measures
				

#### 4.4 Multiplicity Strategy

In the primary analysis, multiplicity will not be an issue since there is only one primary endpoint. For the 2 secondary endpoints, the hypotheses will be tested in the pre-specified order only if the superiority is demonstrated in the primary analysis. Therefore, the type I family-wise error (FWE) for the total of 3 hypothesis tests (primary analysis (once) and secondary analysis (twice)) is controlled (one-sided 2.5%). No hypothesis test is planned for any of the other exploratory endpoints.

#### 4.5 Subgroup Analyses and Effect of Baseline Factors

The consistency of the treatment effect on the primary endpoint will be assessed descriptively using summary statistics by categories of the following subgroup factors:

- Age category (<60, 60-69, 70-79, ≥ 80 years)
- Sex (Female, Male)
- Cataract Grade (Grade 2, Grade 3, Grade 4)

Also, percent ECD change from Visit 0, average torsional amplitude, ██████████  
 ██████████  
 ██████████ will be analyzed in summary statistics by subgroup of cataract grade (Grade 2, Grade 3, Grade 4).

#### 4.6 Interim Analysis for Efficacy

No interim analyses are planned for this study.

## **5 Safety Analysis Strategy**

### **5.1 Safety Endpoints**

The safety endpoints are as below.

- Adverse events
- Device Deficiencies
- Slit Lamp Examination

### **5.2 Safety Hypotheses**

There are no formal safety hypotheses in this study. The focus of the safety analysis will be a comprehensive descriptive assessment of safety endpoints listed in Section 5.1.

### **5.3 Statistical Methods for Safety Analyses**

The analysis set for all safety analyses is defined in Section 2.2. Safety variables after exposure to the test device are listed in Section 5.1. Each safety variable will be summarized descriptively.

#### **5.3.1 Adverse Events**

The number and percentage of eyes with ocular adverse events will be presented by each surgical technique. Also, the number and percentage of subjects with non-ocular adverse events will be presented by investigational technique. An eye with multiple ocular AEs of the same preferred term is only counted once toward the total of this preferred term. Also, a subject with multiple non-ocular AEs of the same preferred term is only counted once toward the total of this preferred term.

Adverse events will be summarized in the following tables by system organ class and preferred level term:

- All Adverse Events (Serious and Non-Serious Combined)
  - Ocular
  - Non-Ocular
- All Adverse Device Effects
  - Ocular
  - Non-Ocular

- All Serious Adverse Events (including Serious Adverse Device Effects)
  - Ocular
  - Non-Ocular
- Any Deaths

Any frequent adverse event that was non-Serious and occurred >5% in one arm will be reported by investigational technique. Also, patient listings will be included for adverse experiences occurred prior to surgery with pre-treatment safety analysis set.

### **5.3.2 Device Deficiencies**

A listing all device deficiencies, as recorded on the Device Deficiency Form will be provided.

### **5.3.3 Slit Lamp Examination**

Number and percentage of presence or not presence of biomicroscopy finding will be tabulated by each surgical technique and by visit. A listing which includes abnormal slit-lamp observations will be provided. The listing will include all slit-lamp data from all visits with the following variables: surgical technique, subject, visit, eye, and slit-lamp observations at the visit.

### **5.4 Interim Analysis for Safety**

No interim analyses are planned for this study.

## **6 Pharmacokinetic Analysis Strategy**

Not Applicable.

## **7 Sample Size and Power Calculations**

The 50 evaluable subjects will be enrolled for this study. For CDE, treatment difference was assumed 1.9% with common standard deviation of 1.2%. The sample size was simulated in Table. 7-1 varying correlation coefficient between both eyes because intra-subject positive correlation between both eyes is assumed for endpoints in this study.

**Table. 7-1 Statistical Power for CDE (N=50)**

Correlation between Both Eyes	Actual Power
-------------------------------	--------------

Correlation between Both Eyes	Actual Power
0	>0.999
0.25	>0.999
0.50	>0.999
0.75	>0.999
0.99	>0.999

Also, for ECD, treatment difference and common standard deviation of ECD percent change from Baseline at Visit 5 was assumed 5.5% with common standard deviation of 11%. The sample size was simulated in Table. 7–2 in the same manner as CDE.

**Table. 7–2 Statistical Power for ECD (N=50)**

Correlation between Both Eyes	Actual Power
0	0.688
0.25	0.808
0.50	0.934
0.75	0.998
0.99	>.999

## 9 Revision History

This is the first revision (Version 2.0) of the Statistical Analysis Plan for this study. This version of the Statistical Analysis Plan is based on Version 2.0 of the study protocol.

The main purpose of this revision (Version 2.0) is to add Modified Full Analysis Set to Efficacy Analysis Sets in Section 2.1.

The other changes are follows;

- In Section 2.1, adding explanation of use of MFAS for sensitivity analysis of primary and secondary endpoints, and
- In Section 4.3, adding primary and secondary endpoints of MFAS to Table 4-1.

Date/Time (mm/dd/yyyy GMT):	Signed by:	Justification:
[REDACTED]	[REDACTED]	[REDACTED]
[REDACTED]	[REDACTED]	[REDACTED]
